STATISTICAL ANALYSIS PLAN WITH RESULTS

Screen to Save: A Colorectal Cancer Educational Intervention

NCT03907579

Date: July 8, 2020

ANALYSIS - BACKGROUND

For the Screen2Save intervention, subjects first take a survey, participate in the intervention and then take a final survey. The questions are the same on both surveys. All analysis was done using Stata/SE 15.1.

DID THE INTERVENTION CHANGE THE SURVEY RESULTS?

We are most interested in whether the subjects scored better (had more correct answers) in the post survey than the pre survey. Thus, for analysis purposes, each question was coded as a dichotomous Correct or Not Correct. If a subject did not submit a response for the question, it was coded as Not Correct (we may want to revisit this).

In order to test whether there was a difference in the Correct responses in the pre and post tests, McNemar's Test was used.

The McNemar test is a non-parametric test for paired nominal data. It's used when you are interested in finding a change in proportion for the paired data. For example, you could use this test to analyze retrospective case-control studies, where each treatment is paired with a control. It could also be used to analyze an experiment where two treatments are given to matched pairs. This test is sometimes referred to as McNemar's Chi-Square test because the test statistic has a chi-square distribution. (<https://www.statisticshowto.com/mcnemar-test/>)

When sample sizes are small, the chi-squared value may not be well-approximated by the chi-squared distribution. The exact p-value can be computed.

Thus, for each pair of pre and post questions, McNemar's Test was performed and both the Chi² and the exact P-value are shown. If the p-value is significant (<0.05), then the null hypothesis (H₀ = the number of correct responses on the pre survey are the same as on the post survey) can be rejected.

HOW DID THE SURVEY RESPONSE CHANGE?

Although the primary interest is whether the intervention increased knowledge about Colorectal cancer and screening, understanding what the specific responses were to the surveys is also of interest. CrossTab tables help to both quantify and visualize the relationship between the Pre and Post responses. The Pre responses are shown in the rows while the Post responses are in the columns. The light green to dark blue color gradient highlights the low to high number of responses for each category.

Did the intervention increase the number of correct answers?

In order to look at the overall impact of the intervention, the number of correct responses was tabulated for each participant pre and post intervention. This data is shown in a CrossTab table. As with the individual questions, no response/null answers were coded as incorrect. In order to test of the number of correct responses was significantly different pre and post intervention, the Wilcoxon Signed-Rank Test was used. This is the non-parametric (i.e. not normally distributed) equivalent of a paired t-test.

SURVEY RESPONSES – WITH McNEMAR'S CHI2 TEST STATISTIC AND EXACT P-VALUE AS WELL AS CROSSTAB

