Correct Answer: True

McNemar's chi2(1) = 2.00 Prob > chi2 = 0.1573

Exact McNemar significance probability = 0.5000

NOT SIGNIFICANT, THERE IS NOT A SIGNIFICANT DIFFERENCE IN THE CORRECT RESPONSES PRE AND POST SURVEY.

		Post Earlier found, greater survival		Grand Total
Pre Earlier Found, greater survival		Null	True	
Null	Null	1	2	3
	True		97	97
Grand Total		1	99	100

8. EVEN IF I HAVE NO SYMPTOMS, I MAY STILL HAVE COLORECTAL CANCER.

Correct Answer: True

McNemar's chi2(1) = 5.40 Prob > chi2 = 0.0201

Exact McNemar significance probability = 0.0352

SIGNIFICANT, THERE IS A SIGNIFICANT DIFFERENCE IN THE CORRECT RESPONSES PRE AND POST SURVEY.

Pre No s..	Null	Post No symptoms		Grand Total
		False	True	
Null	1		8	9
False			4	4
True	2	1	84	87
Grand Total	3	1	96	100

9. POLYPS ARE GROWTHS IN THE LINING OF THE COLON OR RECTUM THAT CAN DEVELOP INTO COLORECTAL CANCER.

Correct Answer: True

McNemar's chi2(1) = 0.00 Prob > chi2 = 1.0000

Exact McNemar significance probability = 1.0000

NOT SIGNIFICANT, THERE IS NOT A SIGNIFICANT DIFFERENCE IN THE CORRECT RESPONSES PRE AND POST SURVEY.

Pre Poly..	Null	Post Polyps are growths		Grand Total
		False	True	
Null		1	2	3
True		1	95	97
Grand Total		2	97	100

10. A COLONOSCOPY CAN BE USED TO FIND POLYPS IN THE COLON AND RECTUM.

Correct Answer: True

McNemar's chi2(1) = 1.00 Prob > chi2 = 0.3173

Exact McNemar significance probability = 1.0000

NOT SIGNIFICANT, THERE IS NOT A SIGNIFICANT DIFFERENCE IN THE CORRECT RESPONSES PRE AND POST SURVEY.

Pre Colo..	Null	Post Colonoscopy finds polyps		Grand Total
		True	False	
Null		1		1
False			1	1
True		98		98
Grand Total		1	99	100

11. A DIET HIGH IN RED MEATS AND PROCESSED MEATS (LUNCH MEATS, HOT DOGS) INCREASES MY CHANCES OF DEVELOPING COLORECTAL CANCER.

Correct Answer: True

McNemar's $\chi^2(1) = 3.00$ Prob > $\chi^2 = 0.0833$

Exact McNemar significance probability = 0.1460

NOT SIGNIFICANT, THERE IS NOT A SIGNIFICANT DIFFERENCE IN THE CORRECT RESPONSES PRE AND POST SURVEY.

Pre Meat..	Null	Post Meat increase cancer		Grand Total
		False	True	
Null	1		5	6
False		2	4	6
True	1	2	85	88
Grand Total	2	4	94	100

12. IT IS OK TO SKIP COLORECTAL CANCER SCREENING IF I DO NOT HAVE ANY SYMPTOMS.

Correct Answer: False

McNemar's chi2(1) = 0.33 Prob > chi2 = 0.5637

Exact McNemar significance probability = 0.7744

NOT SIGNIFICANT, THERE IS NOT A SIGNIFICANT DIFFERENCE IN THE CORRECT RESPONSES PRE AND POST SURVEY.

Pre Skip ..	Null	Post Skip Screening		Grand Total
		False	True	

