Null		1	2	3
False		87	7	94
True		3		3
Grand Total		1	92	100

13. MY CHANCES OF DEVELOPING COLORECTAL CANCER ARE HIGHER IF SOMEONE IN MY IMMEDIATE FAMILY HAS IT OR HAS HAD IT.

Correct Answer: True

McNemar's $\chi^2(1) = 4.50$ Prob > $\chi^2 = 0.0339$

Exact McNemar significance probability = 0.0703

Chi² is significant, but Exact p-value is not significant. Since the Incorrect responses (when added together) have a cellsize <4, then the Exact P-value should be used.

NOT SIGNIFICANT, THERE IS NOT A SIGNIFICANT DIFFERENCE IN THE CORRECT RESPONSES PRE AND POST SURVEY.

Pre Fami..	Null	Post Familial risk		Grand Total
		False	True	
Null	1		3	4
False			4	4
True		1	91	92
Grand Total	1	1	98	100

14. INCREASING MY PHYSICAL ACTIVITY WILL NOT LOWER MY CHANCES OF DEVELOPING COLORECTAL CANCER.

Correct Answer: False

McNemar's $\chi^2(1) = 5.83$ Prob > $\chi^2 = 0.0158$

Exact McNemar significance probability = 0.0241

SIGNIFICANT, THERE IS A SIGNIFICANT DIFFERENCE IN THE CORRECT RESPONSES PRE AND POST SURVEY.

Pre Physi..	Null	Post Physical activity NOT lower risk		Grand Total
		False	True	
Null		1	5	7
False		60	8	68
True		16	9	25
Grand Total		1	81	100

TOTAL NUMBER OF CORRECT ANSWERS

Pre Total..	Post Total Correct Answers							Yes	Grand T..
	8	9	10	11	12	13	Yes		
4		1							1
6			1	1					2
7	1		1				1		3
8	1	1		2	1	1			6
9			2		4				6
10	2	2	4	7	3	4			22
11			2		8	6			16
12				5	9	10			24
13				2	5	5			12
14			1		1	5			7
Yes							1	1	
Grand To..	4	4	11	17	31	32	1	100	

Wilcoxon Signed Rank Test

Sign	Obs	Sum ranks	Expected
Positive	25	1318	2420
Negative	55	3522	2420
Zero	20	210	210
All	100	5050	5050

unadjusted variance 84587.50

adjustment for ties -2388.38

adjustment for zeros -717.50

adjusted variance 81481.63

Ho: preTotalCorrect = postTotalCorrect

z = -3.861

Prob > |z| = 0.0001

SIGNIFICANT, THERE IS A SIGNIFICANT DIFFERENCE IN THE TOTAL CORRECT RESPONSES PRE AND POST SURVEY.

SUMMARY STATISTICS

Pre Total Correct Answers

	Percentiles	Smallest		
1%	2.5	1		
5%	7	4		
10%	8	6	Obs	100
25%	10	6	Sum of Wgt.	100
50%	11		Mean	10.78
75%	12	14	Std. Dev.	2.195404
90%	13	14	Variance	4.819798
95%	14	14	Skewness	-1.335507
99%	14	14	Kurtosis	6.343168

Post Total Correct Answers

	Percentiles	Smallest		
1%	4.5	1		
5%	8.5	8		
10%	10	8	Obs	100
25%	11	8	Sum of Wgt.	100
50%	12		Mean	11.54
75%	13	13	Std. Dev.	1.719878
90%	13	13	Variance	2.95798
95%	13	13	Skewness	-2.702217
99%	13	13	Kurtosis	15.56301

Variable	Obs	Mean	Std. Dev.	Min	Max

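### Fourteen item tests at an unadjusted 0.05: the SIGNIFICANT labels on Questions 8 and 14 do not survive family-wise correction, while Questions 3 to 6 and the overall knowledge gain stand

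*SAP*

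**What the plan says.** The SAP, under the heading asking whether the intervention changed the survey results, scores each question as correct or not and runs McNemar's test on each pre/post pair. It prints a chi-square and an exact p-value for every question and gives one decision rule: "If the p-value is significant (<0.05), then the null hypothesis" is rejected. It does not say which p-value the rule refers to, beyond the general remark "When sample sizes are small, the chi-squared value may not be well-approximated by the chi-squared distribution". Neither the SAP nor the protocol's Analysis section mentions multiplicity.

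On what matters most, the SAP says "the primary interest is whether the intervention increased knowledge about Colorectal cancer and screening". It then introduces a total score with "In order to look at the overall impact of the intervention" and tests it by the Wilcoxon signed-rank test. It does not call that test the main one.

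Of a blank answer, the SAP says "it was coded as Not Correct (we may want to revisit this". The only rule for choosing between the p-values is a note in the Question 13 results, which prefers the exact value because "the Incorrect responses (when added together) have a cellsize <4". Questions 3, 4, 5, 6, 8 and 14 are labelled SIGNIFICANT; the other eight are not.

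**The concern.** Fourteen separate rejections at 0.05 give a much larger chance of some false rejection than 0.05. The SAP neither controls that chance nor tells the reader it is uncontrolled. The six SIGNIFICANT labels look alike, yet the evidence behind them differs greatly. The exact p-values for Questions 3 to 6 are 0.0002 or smaller; those for Question 8 (cancer without symptoms) and Question 14 (physical activity) are 0.0352 and 0.0241.

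What is at stake is limited: whether the report may say that the education changed knowledge on those two specific topics.

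**Working it through.** **Inputs.** Discordant counts come from the SAP crosstabs, with cells lost in text extraction restored from the margins. *Gain* is incorrect to correct; *loss* is correct to incorrect.

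| Question | Gain, loss | Chi-square p | Exact p | Printed label |
|---|---|---|---|---|
| 1 | 13, 13 | 1.0000 | 1.0000 | not significant |
| 2 | 14, 6 | 0.0736 | 0.1153 | not significant |
| 3 | 32, 4 | 0.0000 | 0.0000 | SIGNIFICANT |
| 4 | 13, 0 | 0.0003 | 0.0002 | SIGNIFICANT |
| 5 | 28, 3 | 0.0000 | 0.0000 | SIGNIFICANT |
| 6 | 40, 4 | 0.0000 | 0.0000 | SIGNIFICANT |
| 7 | 2, 0 | 0.1573 | 0.5000 | not significant |
| 8 | 12, 3 | 0.0201 | 0.0352 | SIGNIFICANT |
| 9 | 2, 2 | 1.0000 | 1.0000 | not significant |
| 10 | 1, 0 | 0.3173 | 1.0000 | not significant |
| 11 | 9, 3 | 0.0833 | 0.1460 | not significant |
| 12 | 5, 7 | 0.5637 | 0.7744 | not significant |
| 13 | 7, 1 | 0.0339 | 0.0703 | not significant |
| 14 | 21, 8 | 0.0158 | 0.0241 | SIGNIFICANT |

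**Reproduction.** Chi-square = (gain − loss)² / (gain + loss), without continuity correction; the exact p is the two-sided binomial test on gain + loss. Question 8: 9²/15 = 5.40. Question 14: 13²/29 = 5.83. All 14 printed pairs of p-values reproduce, including "Exact McNemar significance probability = 0.0352" for Question 8. The two p-values fall on opposite sides of 0.05 for Question 13 only. All 14 printed verdicts agree with the exact value.

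**Bonferroni, Questions 3 to 6.** The largest p is Question 4's: 14 × 0.000244 = 0.0034 (exact). With chi-square it is 0.0044.

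**Holm, exact p.** Questions 6, 3, 5 and 4 take ranks 1 to 4.
- Question 14, rank 5: 10 × 0.02412 = 0.241.
- Question 8, rank 6: 9 × 0.03516 = 0.316.
- With chi-square p-values the Holm figures are 0.158 (Question 14) and 0.181 (Question 8), so the choice of p-value does not rescue either.

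**Discrete step-down.** Holm charges in full for tests with too few discordant pairs to reach 0.05 (Questions 7, 9 and 10). A less conservative version adds, over the questions not yet rejected, the null probability of an exact p no larger than the one observed.
- Question 14: 0.0241 (Q14) + 0.0074 (Q8) + 0.0078 (Q13) + 0.0118 (Q2) + 0.0063 (Q11) + 0.0063 (Q12) + 0.0094 (Q1) = 0.073.
- Question 8: 0.0352 (Q8) + 0.0078 (Q13) + 0.0118 (Q2) + 0.0063 (Q11) + 0.0063 (Q12) + 0.0290 (Q1) = 0.096.

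**Chance of a false label among the other ten.** The attainable sizes of the exact test at 0.05, given each question's discordant total, are 0.0290 (Q1), 0.0414 (Q2), 0.0352 (Q8), 0.0386 (Q11), 0.0386 (Q12), 0.0078 (Q13), 0.0241 (Q14), and 0 for Questions 7, 9 and 10. Under independence, 1 − product(1 − size) = 0.196. Under any dependence the bound is the sum, 0.215.

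**Unadjusted 95% Wald intervals.** Change = (gain − loss)/100; standard error = √(gain + loss − (gain − loss)²/100)/100.
- Question 8: 0.09 ± 1.96 × 0.0377, or 2 to 16 points.
- Question 14: 0.13 ± 1.96 × 0.0523, or 3 to 23 points.

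**Blanks.** 8 of Question 8's 12 gains and 5 of Question 14's 21 are blank to correct. Among people who answered both times, Question 8 is 4 against 1 (exact p 0.375) and Question 14 is 16 against 8 (exact p 0.152).

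**Total score.** Pre-test correct counts over the 14 questions sum to 1,078, matching the printed mean of 10.78 × 100. Post-test counts are 69 + 74 + 72 + 92 + 72 + 88 + 99 + 96 + 97 + 99 + 94 + 92 + 98 + 81 = 1,223, but the printed post mean of 11.54 implies 1,154. The gap, 1,223 − 1,154 = 69, equals Question 1's post-test correct count, and the printed post maximum is 13 of 14. Restoring those 69 moves the mean gain from 0.76 to (1,223 − 1,078)/100 = 1.45. A search over how the 69 could fall across participants gave an absolute z between 5.8 and 7.5, against 3.861 printed.

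**The case against.** The best defence is that no label breaks the SAP's own rule. Questions 8 and 14 are below 0.05 on both p-values. Where the two disagree, at Question 13, the SAP says so and takes the more conservative one. The protocol asks about knowledge overall and states no hypothesis for single questions, and in a one-group educational evaluation adjusting secondary items is a choice rather than a requirement. The total-score test also matches the stated primary interest closely. Finally, two of the ten weaker questions were flagged, not one. With the sizes above and independence, two or more false flags would occur only about 1.8% of the time.

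Much of this stands, and it limits the point to reporting. It does not remove it. The SAP pairs a formal rejection rule with a capitalised verdict for each question, which is more than description. The 1.8% speaks to the pair jointly and validates neither question alone.

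A reader might go further in four ways that the documents do not support:
- *The unstated choice of p-value decides Questions 8 and 14.* At 0.05 it changes Question 13 only. It would matter under Benjamini-Hochberg (exact 0.082 and 0.068, chi-square 0.047 and 0.044, for Questions 8 and 14), but neither document uses that criterion.
- *The false-positive chance is 40% to 49%.* Those are chi-square figures, whereas the printed verdicts follow the exact test.
- *The answered-both results show no change.* Question 8 then has five discordant pairs, and even 5 against 0 gives exact p 0.0625, so it could not reach 0.05. A blank that becomes correct may also be real learning.
- *The overall gain is in doubt.* Leaving Question 1 out of the post total alone understates the gain.

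**Conclusion.** The point holds as a correction to reporting. Four of the six SIGNIFICANT labels are secure under family-wise control. The two on Questions 8 and 14 are not, with either p-value and with either Holm or the discrete step-down. The total-score test is the natural main test, but the SAP does not name it so. The overall finding of a knowledge gain is unaffected.

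This rests on treating the 14 questions as one family and on family-wise error as the criterion. The 20% figure further assumes no true change in the ten questions, independence between them, and conditioning on the observed discordant totals; the 21% bound drops independence. The questions share respondents, and a method using their correlation would need participant-level data that the documents do not give. A team that prefers false-discovery control with chi-square p-values could keep both labels, provided it says so.

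**What to change.** 1. State in the methods that the exact McNemar p-value decides for all 14 questions. This changes no printed verdict and makes the Question 13 note unnecessary.
2. Do one of the following.
   - Add a family-wise adjusted column (Holm, noted as conservative for discrete and correlated tests, or the discrete step-down) and mark Questions 8 and 14 as not significant after adjustment.
   - Drop both kinds of verdict, label the items exploratory, and state that p-values and intervals are unadjusted for 14 tests and do not support claims about single questions. The statement is essential: the unadjusted intervals for Questions 8 and 14 exclude zero, so intervals alone would invite the same inference.
3. Correct the post-test total, for which "the number of correct responses was tabulated for each participant pre and post intervention", so that Question 1 is counted. Rerun the Wilcoxon test, the crosstab and the summary statistics. Then name the 14-question total (Wilcoxon signed-rank, two-sided 0.05) as the main test, disclosing that it was designated after the results were known.
4. As a secondary note beside Questions 8 and 14, say that the results depend on counting blanks as incorrect, and that the answered-both figure for Question 8 is too sparse to show absence of change.

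The cost is a few sentences, one column or a relabel, and one rerun on existing data. The downside is that two secondary item claims are lost or softened.

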1. COLORECTAL CANCER STARTS IN WHAT PART OF THE BODY?

Correct Answer: Colon and/or rectum

McNemar's chi2(1) = 0.00 Prob > chi2 = 1.0000

Exact McNemar significance probability = 1.0000

NOT SIGNIFICANT, THERE IS NOT A SIGNIFICANT DIFFERENCE IN THE CORRECT RESPONSES PRE AND POST SURVEY.

Pre Starts in what body part	Post Starts in what body part			Grand Total
	Null	Colon and or rectum	Small Intestine	
Null	2	4	1	7
Colon and or rectum	1	56	10	69
Small Intestine	1	8	10	20
Stomach		1	1	2
Grand Total	4	69	22	100

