preTotalCorrect	100	10.78	2.195404	1	14
postTotalCorrect	100	11.54	1.719878	1	13

The 1st column is Total Correct Answers Post – Pre. So, one person (Freq column) had 4 more correct answers on the pre test and one person had 6 more correct answers Post. In most cases (29), people had one more correct answer.

Post – Pre Total Correct	Freq.	Percent	Cum.
-4	1	1.00	1.00
-2	5	5.00	6.00
-1	19	19.00	25.00
0	20	20.00	45.00
1	29	29.00	74.00
2	9	9.00	83.00
3	11	11.00	94.00
4	2	2.00	96.00
5	3	3.00	99.00
6	1	1.00	100.00
Total	100	100.00	

INTENT

No analysis was done on the intent questions as they were only asked one time.

Intent

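### The post-test total score appears to omit question 1 while the pre-test total includes it, so the overall gain is 1.45 items rather than the 0.76 implied by the SAP

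*SAP*

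**What the plan says.** The SAP's background section says of the two questionnaires: "The questions are the same on both surveys". Each question is scored correct or not correct. For the overall score, "the number of correct responses was tabulated for each participant pre and post intervention", and "no response/null answers were coded as incorrect". Every item therefore adds 0 or 1 to a participant's total.

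Under the total-score heading the SAP gives a pre/post crosstab and a Wilcoxon signed-rank test with z = -3.861 and "Prob > |z| = 0.0001". It concludes: "SIGNIFICANT, THERE IS A SIGNIFICANT DIFFERENCE IN THE TOTAL CORRECT RESPONSES PRE AND POST SURVEY". The summary statistics give a pre-test mean of 10.78 (maximum 14) and a post-test mean of 11.54 (maximum 13). A table of post-minus-pre changes follows, with the comment "In most cases (29), people had one more correct answer". The SAP nowhere says that a question was left out of either total.

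**The concern.** With 14 questions scored 0 or 1, the item correct counts must sum to 100 times the mean total. This holds for the pre-test and fails for the post-test. A maximum of 13 also looks odd: 32 people sit at 13 after the intervention and nobody reaches 14, although 7 people scored 14 beforehand.

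The total score is the SAP's only measure of overall impact, and the protocol's Analysis section sets out to evaluate change in knowledge. If one item is missing from the post-test total only, everyone who got it right afterwards loses a point. The gain shrinks, the number recorded as worse may be inflated, and anyone with a pre-test score of 14 must show a decline.

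**Working it through.** **Inputs.** Correct counts out of 100, from the margins of the SAP's item tables:

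| Question | Pre | Post |
|---|---|---|
| 1 | 69 | 69 |
| 2 | 66 | 74 |
| 3 | 44 | 72 |
| 4 | 79 | 92 |
| 5 | 47 | 72 |
| 6 | 52 | 88 |
| 7 | 97 | 99 |
| 8 | 87 | 96 |
| 9 | 97 | 97 |
| 10 | 98 | 99 |
| 11 | 88 | 94 |
| 12 | 94 | 92 |
| 13 | 92 | 98 |
| 14 | 68 | 81 |
| **Sum** | **1078** | **1223** |

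Some tables are broken in the extracted text, so each pair of counts was checked against that item's McNemar chi-squared and exact p. All 14 agree. For question 1 ("COLORECTAL CANCER STARTS IN WHAT PART OF THE BODY"), the printed post-test column for the correct answer adds up (4 + 56 + 8 + 1 = 69). The discordant counts are 69 - 56 = 13 each way, which gives the reported chi-squared of 0.00.

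**Reproducing the SAP's test.** The change table sums to -4 - 10 - 19 + 0 + 29 + 18 + 33 + 8 + 15 + 6 = 76, a mean of 0.76 = 11.54 - 10.78. Ranking the absolute changes with zeros included gives:

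- gains: 29×44.5 + 9×75.5 + 11×88 + 2×95 + 3×98 + 1×100 = 3522
- losses: 19×44.5 + 5×75.5 + 1×95 = 1318
- |z| = (3522 - 2420)/√81481.63 = 3.861

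These are the published figures. The test was computed correctly on the totals supplied to it.

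**Checking the totals.** The entry labelled Yes in the crosstab is read as 1, the minimum in the summary statistics.

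- Pre: 1 + 4 + 2×6 + 3×7 + 6×8 + 6×9 + 22×10 + 16×11 + 24×12 + 12×13 + 7×14 = 1078. This equals the item sum.
- Post: 1 + 4×8 + 4×9 + 11×10 + 17×11 + 31×12 + 32×13 = 1154. The item sum is 1223.
- Shortfall: 1223 - 1154 = 69.

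Only question 1 has 69 correct on the post-test. The next lowest counts are 72 (questions 3 and 5). No two items could together account for 69, because 69 is the smallest count.

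**Size of the error.**

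- 14 items on both sides: 12.23 - 10.78 = 1.45.
- 13 items on both sides: 11.54 - (1078 - 69)/100 = 11.54 - 10.09 = 1.45.
- 0.76/1.45 = 0.52, so 48% of the gain is lost.

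**Effect on the test.** Participant data are not given, so who gains the missing point is unknown. Adding 1 to 69 of the 100 published changes gives:

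- Improved: 55 (none of the 20 ties gains the point) to 75 (all do); published 55.
- Worse: 25 (none of the 19 at -1 gains it) to 6 (all do); published 25.
- |z|: 5.79 to 7.55, found by search over allocations.
- If gaining the point is unrelated to the published change (an assumption): |z| about 6.6, improved about 55 + 0.69×20 = 69, worse about 25 - 0.69×19 = 12.

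Dropping question 1 from both totals also adds 69 points to the change table, this time to those with question 1 right on the pre-test. The same outer limits therefore apply.

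**The case against.** Four points can be made on the other side.

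- **The omission is inferred.** Neither the code nor participant data are shown. This stands as a caveat. But the match is exact and unique, and the maximum of 13 fits it. Scoring question 1 as wrong for everyone in the post-test total would have the same effect and need the same correction.
- **The conclusion does not change.** This also stands. The error is conservative, p stays below 0.0001 under every allocation examined, and the 14 item-level McNemar tests are untouched. What is wrong is the size of the effect and every total-score figure involving the post-test.
- **The two remedies are not identical.** They give the same mean gain, but 26 participants changed status on question 1, so z and the improved/worse counts can differ. One version has to be chosen and stated.
- **Some declines may be real.** Of the 7 people with a pre-test score of 14, the two with post-test totals of 10 and 12 remain worse even with an added point. The five at 13 would tie on a 14-item score only if they had question 1 right afterwards, which is not known. On a 13-item score for both surveys those five are ties for certain.

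**Conclusion.** The concern holds. The published post-test total is 69 points below the SAP's own item tables, and omission of question 1 accounts for the gap exactly. The mean gain is 1.45 items, not 0.76. The Wilcoxon statistic, rank sums, 55/20/25 split, post-test summary statistics, total-score crosstab and change table all rest on a 13-item post-test score set against a 14-item pre-test score. The significance verdict is unaffected and would be strengthened. The mean gain follows directly from printed margins. The corrected z and counts are known only as ranges until participant data are used. The upper and lower ends of those ranges are extremes, not likely values.

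**What to change.** Rebuild postTotalCorrect over all 14 questions, confirming in the code that question 1 was missing or mis-scored. Dropping question 1 from both totals is an acceptable alternative, but the SAP should say which score is used. Then:

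- rerun the Wilcoxon test, total-score crosstab, summary statistics and post-minus-pre table;
- state the mean change (1.45) and the corrected numbers improved, unchanged and worse;
- add a check that item correct counts sum to the total-score sum on each survey;
- correct any report that carries the present figures.

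The cost should be a small code change and a rerun of one section, with no new data.
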